## 5. CONSIDERATIONS FOR DATA ANALYSES AND DATA HANDLING CONVENTIONS

Table 1 provides an overview of appendices within the RAP for outlining general considerations for data analyses and data handling conventions. A full set of appendices is provided in Section 11.

**Table 1 Overview of Appendices**

Section	Component
11.1	Appendix 1: Protocol Deviation Management and Definitions for Per Protocol Population
11.2	Appendix 2: Time & Events
11.3	Appendix 3: Assessment Windows
11.4	Appendix 4: Treatment States and Phases
11.5	Appendix 5: Data Display Standards & Handling Conventions
11.6	Appendix 6: Derived and Transformed Data
11.7	Appendix 7: Premature Withdrawals & Handling of Missing Data
11.8	Appendix 8: Adverse Event Time Periods and Special Adverse Event Definitions
11.9	Appendix 9: Values of Potential Clinical Importance
11.10	Appendix 10: Multicenter Studies
11.11	Appendix 11: Examination of Covariates, Subgroups & Other Strata
11.12	Appendix 12: Multiple Comparisons & Multiplicity
11.13	Appendix 13: Model Checking and Diagnostics for Statistical Analyses.
11.14	Appendix 14: Abbreviations and Trademarks
11.15	Appendix 15: List of Data Displays
11.16	Appendix 16: Example Mock Shells for Data Displays
11.17	Appendix 17: Amendment 01 Revisions

## 6. STUDY POPULATION ANALYSES

### 6.1. Overview of Planned Analyses

The study population analyses will be based on the Evaluable subjects, unless otherwise specified.

Table 2 provides an overview of the planned study population summaries and listings, with full details of planned data displays being presented in Appendix 15: List of Data Displays. All summaries will be presented by the following categories: IPSS $\geq$ 8, BPE/BPO $\geq$ 3, IPSS $\geq$ 8 and BPE/BPO $\geq$ 3, and IPSS $\geq$ 8 or BPE/BPO $\geq$ 3, unless otherwise noted.

Formal hypothesis testing will not be performed in terms of the study population data.

**Table 2 Overview of Planned Study Population Analyses**

Display Type	Data Displays Generated		
	Table	Figure	Listing
Subject Accountability			
Numbers of Subjects, including Screened, Screened But Not Evaluable, and Evaluable	Y		
Number of Subjects, including: Evaluable, Evaluable with PSA Values (<2 or $\geq$ 2), GP Assessments, and Urologist Assessments	Y		Y
Subject Disposition			
Overall Disposition	Y		Y
Subject Withdrawals	Y		Y
Discontinuation by Visit	Y		
Inclusion / Exclusion Criteria Deviations (Screened But Not Evaluable Subjects)	Y		Y
Important Protocol Deviations	Y		Y
Demographic Characteristics			
Demographic Characteristics	Y		Y
Race	Y		Y
Medical Conditions and Concomitant Medications			
Medical Conditions by Body System	Y		Y
Surgical / Diagnostic Procedures	Y		Y
Concomitant Medications	Y		Y
Diagnostic Tests and Questionnaires			
PSA	Y		
IPSS and BPE/BPO	Y		

**NOTES :**

- Y = Yes display generated.
- There are no planned Study Population Figures.

## 6.2. Subject Accountability

Summaries for the following will be produced in terms of total number overall:

- All Screened Subjects
- All Evaluable Subjects

Evaluable subjects include those subjects who met all inclusion and exclusion criteria including a positive IPSS (score $\geq$ 8) and/or BPE/BPO (score $\geq$ 3). Summaries for the Screened and Evaluable subjects will also be presented by country, and separately by country and center.

A summary table will be produced for the screened subjects and will contain the following:

- Number of subjects who were sScreened but not Evaluable
- Number of subjects who were Evaluable

A summary of screened subjects by country, and separately by country and center will also be presented.

A summary table will be produced for the Evaluable subjects and will contain the following:

- All Evaluable Subjects (IPSS $\geq$ 8 or BPE/BPO $\geq$ 3)
- Evaluable Subjects with PSA $<$ 2.0ng/mL
- Evaluable Subjects with PSA $\geq$ 2.0ng/mL
- Evaluable Subjects with Any GP Assessment of BPH
- Evaluable Subjects with GP Assessment of BPH="Yes"
- Evaluable Subjects with GP Assessment of BPH="No"
- Evaluable Subjects with GP Assessment of BPH="Yes" and Urologist Assessment of BPH
- Evaluable Subjects with GP Assessment of BPH="Yes" and Urologist Assessment of BPH="Yes"
- Evaluable Subjects with GP Assessment of BPH="Yes" and Urologist Assessment of BPH="No"
- Evaluable Subjects with GP Assessment of BPH="Yes" and Any Urologist Risk Assessment of BPH Progression
- Evaluable Subjects with GP Assessment of BPH="Yes" and Urologist Risk Assessment of BPH Progression="Yes"
- Evaluable Subjects with GP Assessment of BPH="Yes" and Urologist Risk Assessment of BPH Progression="No"

An overall summary and the data above will also be presented by country, and separately by country and center for the Evaluable subjects.

### 6.3. Subject Disposition

A subject may withdraw from the study at any time at the investigator's discretion or at the request of the subject.

The reason for study withdrawal is recorded in the eCRF for Evaluable subjects who prematurely withdrew from the study prior to completing Visits 1, 2, and 3. A tabular summary will be produced for number and percentage of subjects prematurely withdrawing from the study, overall and by reason. Additional tabular summaries will be produced by Visit (overall and by reason) for subjects withdrawing from the study. For these summaries, the percentages are calculated using the number of subjects in each of the categories (IPSS $\geq$ 8, BPE/BPO $\geq$ 3, IPSS $\geq$ 8 and BPE/BPO $\geq$ 3, and IPSS $\geq$ 8 or BPE/BPO $\geq$ 3) as the denominators.

Listings will be produced for subject disposition and reason for withdrawal and will include key accountability data including study status, completion or withdrawal date, all visit dates, and the primary reason for premature withdrawal.

### 6.4. Demographic Characteristics

The following demographic characteristics will be summarized for the Screened But Not Evaluable and Evaluable subjects; summaries for the Evaluable subjects will be repeated by country, and separately by country and center:

- Sex
- Age in years
- Age categories (years): <65,  $\geq$ 65, <75,  $\geq$ 75
- Race (Evaluable subjects only)

Listings will be produced for sex, age, and race (Evaluable subjects only). Race information will not be presented in tables or listings for subjects who were enrolled in the study in France.

### 6.5. Medical Conditions, Surgical Procedures, and Concomitant Medications

The following medical conditions and surgical procedures are GSK standardized data collections and/or are of interest in terms of the Evaluable subjects, and will be summarized in tabular and listing formats. The number and percentage of subjects reporting having each medical condition or surgical procedure will be included in the summary. Tabular summaries of surgical procedures will be presented for screening and post-screening visits.

#### Medical Conditions

- Cardiovascular Risk Factors
  - Angina Pectoris
  - Myocardial Infarction

- Stroke
- Diabetes
- Hypertension
- Hyperlipidemia
  
- Urinary Conditions
  - Incomplete Urination
  - Unable to Urinate
  - Urination Difficulty
  - Micturition Disorder
  - Increased Urinary Frequency
  - Recurrent Urinary Tract Infection
  - Hematuria
  - Urinary Incontinence Surgery
  - Urethral Stricture
  - Urine Flow Decreased
  - Post Void Dribbling
  - Nocturia
  - Urinary Calculus
  - Bladder Neoplasm/Tumor

#### Surgical Procedures

- Cystoscopy
- Transrectal Ultrasound
- Prostate Biopsy
- Ultrasound Abdomen
- Computerized Tomogram Abdomen
- Computerized Tomogram Pelvis
- Nuclear MRI Abdominal
- Pelvic MRI
- Renal Scan
- Bladder Scan
- Abdominal X-Ray
- Other

Concomitant medication data are collected on eCRF log forms and will be coded using the GSKDrug dictionary. Concomitant medications will be defined as any medication documented as such in the database, irrespective of start or stop dates or ongoing status.

A summary of concomitant medications will be provided. The number and percentage of subjects reporting the use of each concomitant medication will be summarized and will include ATC Level I and ingredient. A listing of the collected concomitant medications by country and center will be provided. A listing of the relationship between the ATC Level I, ingredient, and verbatim text for concomitant medications will also be provided.

## 6.6. Diagnostic Tests and Questionnaires

The IPSS screening tool is completed at the screening visit. The total IPSS score is the sum of the 7 individual questions. The total IPSS score will be summarized by N, Mean, Standard Deviation, Median, Minimum, and Maximum. The number and percentage of subjects with total IPSS scores will also be summarized categorically using the following categories: <8, 8 – 19, >19.

The BPE/BPO screening tool is completed at the screening visit. The total BPE/BPO score is the sum of the 3 individual questions. The total BPE/BPO score will be summarized by N, Mean, Standard Deviation, Median, Minimum, and Maximum. The number and percentage of subjects with total BPE/BPO scores will also be summarized categorically using the following categories: <3, 3 – 6, >6.

Serum PSA samples are scheduled at the screening visit after the subject is enrolled. Serum PSA will be summarized by N, Mean, Standard Deviation, Median, Minimum, and Maximum. The number and percentage of subjects with serum PSA data will also be summarized categorically using the following categories: <2, 2 – 9, >9.

The IPSS, BPE/BPO, and PSA data described above will also be summarized by country, and separately by country and center.

## 7. PRIMARY STATISTICAL ANALYSES

### 7.1. Primary Efficacy Analyses

#### 7.1.1. Overview of Planned Primary Efficacy Analyses

The primary endpoint is defined as the proportion of men confirmed to have BPH based on full Urologist diagnostic testing among men with a positive result on the BPE/BPO screening tool (score  $\geq 3$ ) and serum PSA  $\geq 2$  ng/mL. The BPE/BPO questionnaire consists of three questions each with a score ranging from 0 to 5. This questionnaire is administered at the screening visit (Visit 1).

BPE/BPO (also called the BPE/BPO total score) is the sum of the three questions. BPE/BPO summaries will be in terms of the total (score); exceptions will be noted such as for supporting summaries of individual questions. For calculation of the BPE/BPO total, missing individual responses will not be imputed.

The primary efficacy analyses will be based on the Evaluable subjects, unless otherwise specified. [Table 3](#) provides an overview of the planned BPE/BPO summaries and primary efficacy analyses, with full details of data displays being presented in [Appendix 15: List of Data Displays](#).

**Table 3 Overview of Planned Primary Efficacy Analyses**

Endpoint	Stats Analysis			Absolute			
				Summary		Individual	
	T	F	L	T	F	F	L
Proportion of Men with BPH Based on full Urologist Diagnosis and BPE/BPO Score (<math>\geq 3</math>)							
Primary Analysis	Y 						
Supporting Data for Primary Endpoint							
BPE/BPO Individual and Total Scores at Visit 1				Y 			Y 
Summary of PSA Values				Y 			Y 

**NOTES :**

- T = Table, F = Figure, L = Listing, Y = Yes display generated.
- Stats Analysis = Represents TFL related to any formal statistical analyses conducted.
- Summary = Represents TFL related to any summaries (i.e. descriptive statistics) of the observed raw data.
- Individual = Represents FL related to any displays of individual subject observed raw data.
  1. Primary efficacy analyses are presented within this table; details of the analysis are in the following section.
  2. Individual BPE/BPO question 1-3 responses and total scores support the primary analysis; total scores are also presented by country, and separately by country and center.
  3. The PSA summary data supports the primary analysis; the PSA data Tables and Listings appear with the Safety Tables and Listings.

**7.1.2. Planned Primary Efficacy Statistical Analyses**

Primary Statistical Analyses			
Endpoint(s)			

 
Proportion of men that are confirmed to have BPH based on full Urologist assessment of diagnostic test results among men with a positive result on the BPE/BPO screening tool (score <math>\geq 3</math>) and serum PSA <math>\geq 2</math> ng/mL.
 
Primary endpoint summaries will be descriptively presented in terms of the calculated proportion, described below, and 95% confidence interval on the proportion. Formal hypothesis testing will not be conducted.
 
			
Tool	Proportion	Numerator	Denominator
BPE/BPO	BPH diagnosis by Urologist based upon BPE/BPO screening tool (score $\geq 3$ ) and serum PSA $\geq 2$ ng/mL.	Number of subjects diagnosed with BPH based upon a BPH assessment by Urologist.	Number of subjects with a positive result on the BPE/BPO screening tool (score $\geq 3$ ) and serum PSA $\geq 2$ ng/mL and a BPH assessment by Urologist.

 
Table 3 provides an overview of the planned summaries and primary efficacy analyses. A list of planned data displays is in Appendix 15: List of Data Displays.
 
			
Model Specification			

 
No models were used during the statistical analysis; proportions and confidence intervals were computed.
 
			
Model Checking & Diagnostics			

 
Not Applicable
 
			
Model Results Presentation			

 
Not Applicable
 
			
Sensitivity and Supportive Statistical Analyses			

 
Not Applicable
 
			

## 8. SECONDARY STATISTICAL ANALYSES

### 8.1. Secondary Efficacy Analyses

#### 8.1.1. Overview of Planned Secondary Efficacy Analyses

The secondary efficacy analyses will be based on the Evaluable subjects, unless otherwise specified. [Table 4](#) provides an overview of the planned secondary efficacy analyses, with further details of data displays being presented in [Appendix 15: List of Data Displays](#).

**Table 4 Overview of Planned Secondary Efficacy Analyses**

Endpoint	Stats Analysis			Absolute			
				Summary		Individual	
	T	F	L	T	F	F	L
IPSS							
Total and individual scores at Visit 1				Y			Y
BPH-Related Health Status							
Scores at Visit 1				Y			Y
BPE/BPO							
Total and individual scores at Visit 1				Y			Y
Summary of BPH Diagnosis by Urologist, Summary of BPH Progression Risk by Urologist, and Summary of Probable BPH Diagnosis by GP							
Based upon BPE/BPO score ( $\geq 3$ )	Y						
Based upon IPSS score ( $\geq 8$ )	Y						
Based upon IPSS score ( $\geq 8$ ) or BPE/BPO score ( $\geq 3$ )	Y						
Based upon IPSS score ( $\geq 8$ ) and BPE/BPO score ( $\geq 3$ )	Y						
Summary of Subjects Who Discontinued From the Study Before the GP Was Able to Assess the Presence of Probable BPH and Summary of Subjects Who Withdrew from the Study Before a Urologist Visit, Among Subjects Who Were Eligible for Such a Visit							
Based upon BPE/BPO score ( $\geq 3$ )	Y						
Based upon IPSS score ( $\geq 8$ )	Y						
Based upon IPSS score ( $\geq 8$ ) or BPE/BPO score ( $\geq 3$ )	Y						
Based upon IPSS score ( $\geq 8$ ) and BPE/BPO score ( $\geq 3$ )	Y						

Endpoint	Stats Analysis			Absolute			
				Summary		Individual	
	T	F	L	T	F	F	L
BPE/BPO and IPSS							
Summary of agreement between screening tools (Kappa statistic)	Y						
Figures (All Evaluable Subjects)							
Plot of IPSS Scores versus BPE/BPO Scores at Visit 1					Y		
Plot of IPSS Scores versus PSA Values at Visit 1					Y		
Plot of BPE/BPO Scores versus PSA Values at Visit 1					Y		

**NOTES :**

- T = Table, F = Figure, L = Listing, Y = Yes display generated.
- Stats Analysis = Represents TFL related to any formal statistical analyses conducted.
- Summary = Represents TFL related to any summaries (i.e. descriptive statistics) of the observed raw data.
- Individual = Represents FL related to any displays of individual subject observed raw data.
  1. Summary of BPH diagnosis by the Urologist based upon the BPE/BPO screening tool (score  $\geq 3$ ) is a Primary Endpoint and is not included in the Secondary Endpoint analysis.

**8.1.2. Planned Secondary Efficacy Statistical Analyses**

Primary Statistical Analyses			
Endpoint(s)			
Secondary endpoints and other measures of interest are defined in terms of proportions for each: probable BPH diagnosis by GP, BPH diagnosis by Urologist, and BPH progression risk by Urologist along with use of 1) BPE/BPO screening tool and 2) IPSS screening tool. The 95% confidence intervals (calculated using the exact (Clopper-Pearson) method) for these proportions will be presented.			
Secondary Endpoints: Proportions only in terms of the BPE/BPO tool			
Tool	Proportion	Numerator	Denominator
BPE/BPO	BPH Progression Risk by Urologist based upon BPE/BPO screening tool (score $\geq 3$ ) and serum PSA $\geq 2$ ng/mL	Number of subjects diagnosed with BPH progression risk by Urologist	Number of subjects with a positive result on the BPE/BPO screening tool (score $\geq 3$ ) and serum PSA $\geq 2$ ng/mL and a BPH progression risk assessment by Urologist
BPE/BPO	Probable BPH Diagnosis by GP based upon BPE/BPO screening tool (score $\geq 3$ )	Number of subjects diagnosed with 'probable BPH' by GP	Number of subjects with a positive result on the BPE/BPO screening tool (score $\geq 3$ ) and a BPH assessment by GP

Primary Statistical Analyses			
Secondary Endpoints: Proportions only in terms of the IPSS screening tool			
Tool	Proportion	Numerator	Denominator
IPSS	BPH Diagnosis by Urologist based upon IPSS (score $\geq 8$ ) and serum PSA $\geq 2$ ng/mL	Number of subjects diagnosed with BPH based upon BPH assessment by Urologist.	Number of subjects with a positive result on the IPSS (score $\geq 8$ ) and serum PSA $\geq 2$ ng/mL and a BPH assessment by Urologist
IPSS	BPH Progression Risk by Urologist based upon IPSS (score $\geq 8$ ) and serum PSA $\geq 2$ ng/mL	Number of subjects diagnosed with BPH progression risk by Urologist	Number of subjects with a positive result on the IPSS (score $\geq 8$ ) and serum PSA $\geq 2$ ng/mL and a BPH progression risk assessment by Urologist
IPSS	Probable BPH Diagnosis by GP based upon IPSS (score $\geq 8$ )	Number of subjects diagnosed with 'probable BPH' by GP	Number of subjects with a positive result on the IPSS (score $\geq 8$ ) and a BPH assessment by GP

 
Additional summaries, proportions and related 95% confidence intervals, will be generated as outlined above, but in terms of a positive result for both the BPE/BPO and the IPSS screening tools and separately for either the BPE/BPO or IPSS screening tools.
 
Another secondary endpoint of this study is to assess the level of agreement (via the kappa statistic) between the BPE/BPO and/or IPSS screening tools for selecting men to investigate for BPH. The number and proportion of subjects with a positive or with a negative response to both the BPE/BPO and IPSS screening tools at screening will be summarized.
 
The kappa coefficient will be characterized as proposed by Landis and Koch (Landis, 1977) with <math><0</math> indicating no agreement, 0-0.20 as slight, 0.21-0.40 as fair, 0.41-0.60 as moderate, 0.61-0.80 as substantial, and 0.81 – 1 as almost perfect agreement.
 
The proportion of subjects who discontinued from the study before the GP was able to assess the presence of probable BPH will be summarized. The proportion of subjects who withdrew from the study before a Urologist visit, among subjects with a probable GP BPH diagnosis will be summarized.
 
			
Model Specification			

 
No models were used during the statistical analysis; proportions and confidence intervals were computed.
 
			
Model Checking & Diagnostics			

 
Not Applicable
 
			
Model Results Presentation			

 
Not Applicable
 
			
Sensitivity and Supportive Statistical Analyses			

 
Not Applicable
 
			

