## **8.4. Key Elements of Analysis Plan**

Data will be listed and summarized according to GSK reporting standards, where applicable. Complete details will be documented in the RAP. Any deviations from, or additions to, the original analysis plan described in the protocol will be documented in the RAP and final study report.

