Additional summaries, proportions and related 95% confidence intervals, will be generated as outlined above, but in terms of a positive result for both the BPE/BPO and the IPSS screening tools.

Another secondary endpoint of this study is to assess the level of agreement between the BPE/BPO and/or IPSS screening tools for selecting men to investigate for BPH. The number and proportion of subjects with a positive or with a negative response to both the BPE/BPO and IPSS screening tools at screening will be summarized.

Agreement of the BPE/BPO and the IPSS screening tools will be assessed using the kappa coefficient. The simple kappa coefficient along with the 95% confidence interval will be generated using SAS along with hypothesis testing. The associated null hypothesis is that the two measures (BPE/BPO and IPSS screening tools) are independent, i.e.,  $\kappa = 0$ . The alternative hypothesis is that the agreement of the two measures is better than one would expect by chance. Two-sided tests of the null hypothesis will be conducted at the 0.05 level of significance.

The above defined kappa coefficient will be characterized as proposed by Landis and Koch (Landis, 1977) with  $<0$  indicating no agreement, 0-0.20 as slight, 0.21-0.40 as fair, 0.41-0.60 as moderate, 0.61-0.80 as substantial, and 0.81 – 1 as almost perfect agreement.

The proportion of men refusing further GP investigation among subjects with a positive BPE/BPO screening tool will be summarized. The proportion of subjects refusing referral to an urologist among subjects with a positive BPE/BPO screening tool and probable GP BPH diagnosis will be summarized.

The above described proportions, for both primary and secondary endpoints, will also be summarized by country.

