## 2. SUMMARY OF KEY PROTOCOL INFORMATION

### 2.1. Changes to the Protocol Defined Statistical Analysis Plan

There were no changes or deviations to the originally planned statistical analysis specified in Protocol Amendment 2 (Dated: 18/Jan/2016).

This document contains the RAP amendment 01 which is based on the protocol amendment 2 noted above. RAP amendment 01 revisions primarily include redefining the Screened But Not Enrolled and the Enrolled study populations. These study populations will now be defined as the Screened But Not Evaluable and Evaluable populations. This amendment 01 includes no major changes to the planned analyses. The summary of RAP amendment 01 changes is contained in [Appendix 17](#).

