2.40.	All Evaluable Subjects	Summary of Probable BPH Diagnosis by GP Based Upon IPSS Score ( $\geq 8$ )
2.41.	All Evaluable Subjects	Summary of Probable BPH Diagnosis by GP Based Upon IPSS Score ( $\geq 8$ ) by Country
2.42.	All Evaluable Subjects	Summary of Probable BPH Diagnosis by GP Based Upon IPSS Score ( $\geq 8$ ) by Country and Center
2.43.	All Evaluable Subjects	Summary of Probable BPH Diagnosis by GP Based Upon IPSS Score ( $\geq 8$ ) or BPE/BPO Score ( $\geq 3$ )

Efficacy: Tables		
No	Population	Title
2.44.	All Evaluable Subjects	Summary of Probable BPH Diagnosis by GP Based Upon IPSS Score ( $\geq 8$ ) or BPE/BPO Score ( $\geq 3$ ) by Country
2.45.	All Evaluable Subjects	Summary of Probable BPH Diagnosis by GP Based Upon IPSS Score ( $\geq 8$ ) or BPE/BPO Score ( $\geq 3$ ) by Country and Center
2.46.	All Evaluable Subjects	Summary of Probable BPH Diagnosis by GP Based Upon IPSS Score ( $\geq 8$ ) and BPE/BPO Score ( $\geq 3$ )
2.47.	All Evaluable Subjects	Summary of Probable BPH Diagnosis by GP Based Upon IPSS Score ( $\geq 8$ ) and BPE/BPO Score ( $\geq 3$ ) by Country
2.48.	All Evaluable Subjects	Summary of Probable BPH Diagnosis by GP Based Upon IPSS Score ( $\geq 8$ ) and BPE/BPO Score ( $\geq 3$ ) by Country and Center
2.49.	All Evaluable Subjects	Summary of Subjects Who Discontinued From the Study Before the GP Was Able to Assess the Presence of Probable BPH
2.50.	All Evaluable Subjects	Summary of Subjects Who Discontinued From the Study Before the GP Was Able to Assess the Presence of Probable BPH by Country
2.51.	All Evaluable Subjects	Summary of Subjects Who Discontinued From the Study Before the GP Was Able to Assess the Presence of Probable BPH by Country and Center
2.52.	All Evaluable Subjects	Summary of Subjects Who Withdrew From the Study Before a Urologist Visit, Among Subjects Who Were Eligible for Such a Visit
2.53.	All Evaluable Subjects	Summary of Subjects Who Withdrew From the Study Before a Urologist Visit, Among Subjects Who Were Eligible for Such a Visit by Country
2.54.	All Evaluable Subjects	Summary of Subjects Who Withdrew From the Study Before a Urologist Visit, Among Subjects Who Were Eligible for Such a Visit by Country and Center

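### SAP 8.1.2 replaces the protocol's two refusal proportions with withdrawal proportions not restricted by reason, while SAP 2.1 declares no change

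*SAP*

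**What the plan says.** Protocol 8.4.3 (Secondary Analyses) commits to two refusal measures. At the GP stage: "The proportion of men refusing further GP investigation among subjects with a positive BPE/BPO screening tool will be summarized". At the urologist stage: "The proportion of subjects refusing referral to an urologist among subjects with a positive BPE/BPO screening tool and probable GP BPH diagnosis will be summarized".

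SAP 8.1.2, at the corresponding place, has two different sentences. At the GP stage: "The proportion of subjects who discontinued from the study before the GP was able to assess the presence of probable BPH will be summarized". At the urologist stage: "The proportion of subjects who withdrew from the study before a Urologist visit, among subjects with a probable GP BPH diagnosis will be summarized". The SAP synopsis (Section 1) repeats both, and Tables 2.49 to 2.54 implement them. The titles of Tables 2.52 to 2.54 describe the second denominator differently: "Summary of Subjects Who Withdrew From the Study Before a Urologist Visit, Among Subjects Who Were Eligible for Such a Visit". SAP Table 4 uses the same description and splits both measures by tool category, including BPE/BPO ≥3.

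On changes to the plan, protocol 8.4 says: "Any deviations from, or additions to, the original analysis plan described in the protocol will be documented in the RAP and final study report". SAP 2.1 says: "There were no changes or deviations to the originally planned statistical analysis specified in Protocol Amendment 2".

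**The concern.** Refusing a test or a referral is a decision by the patient. Leaving the study before a visit is an outcome with several causes, of which refusal is one. The SAP has moved from the first to the second without saying so.

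The refusal measures have a purpose in this study. Protocol 4.1 sets out to reproduce opportunistic screening, and protocol 2.1 describes men who may be reluctant to raise urinary symptoms with their GP. Protocol 4.1 also names men who refuse urologist referral as a group and says how they are to be classified. A table that adds together refusal, loss to follow-up and investigator decisions does not show how many men turned the next step down. If it is reported in place of the protocol measure under a no-change statement, readers may take the withdrawal figure for the refusal figure.

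**Working it through.** **1. The two plans side by side.**

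| Stage | Protocol 8.4.3 | SAP 8.1.2 and Tables 2.49–2.54 |
|---|---|---|
| GP: numerator | refused further GP investigation | left the study before the GP could judge probable BPH |
| GP: denominator | BPE/BPO-positive men | not stated in the sentence; Table 4 splits by tool category, including BPE/BPO ≥3 |
| Urologist: numerator | refused referral | withdrew before the urologist visit |
| Urologist: denominator | BPE/BPO-positive men with GP probable BPH | men with GP probable BPH (text) or men eligible for the visit (titles), split by tool category |

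Table 4 keeps the conditioning on a positive BPE/BPO result. What changed is the numerator.

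**2. Do the numerators coincide?** Protocol 5.4 lets a man withdraw at his own request, lets the investigator withdraw him, and treats a man who cannot be reached as withdrawn with loss to follow-up as the primary reason. Assume every refuser is recorded as withdrawn. Then, at each stage,

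withdrawn = refused + withdrawn for other reasons.

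The SAP figure equals the protocol figure only if the last term is zero.

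**3. Is the change declared?** SAP 2.1 declares none. SAP Appendix 17, which lists the amendment 01 revisions, does not mention it.

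**4. Can refusal be recovered elsewhere in the SAP?** SAP 6.3 plans withdrawals by reason, overall and by visit, as percentages of each tool category. Table 1.13 gives the primary reason by period, and Listing 1.4 lists reasons.

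- *GP stage.* The BPE/BPO ≥3 denominator in SAP 6.3 matches the protocol's. The proportion can be read off if refusal is a recorded reason.
- *Urologist stage.* The SAP 6.3 denominator is all men in the tool category, not those with GP probable BPH. If a share q of BPE/BPO-positive men have GP probable BPH, a referral-refusal rate r appears as r × q. With r = 10% and q assumed between 40% and 80%, the table would show 0.10 × 0.40 = 4% to 0.10 × 0.80 = 8%. A reader could rebuild the protocol figure from the by-reason count and the GP-yes count in SAP 6.2, again only if refusal is recorded.

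The documents do not show the eCRF reason categories, so that condition cannot be checked.

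**5. Possible size (assumed counts).** The documents give no refusal or withdrawal rate, so there is no plan figure to reproduce. Take 500 BPE/BPO-positive men with GP probable BPH, of whom 100 withdraw before the urologist visit. The exact (Clopper-Pearson) 95% limits for x out of n are the 0.025 quantile of Beta(x, n − x + 1) and the 0.975 quantile of Beta(x + 1, n − x).

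| Quantity | x/n | Proportion | Exact 95% CI |
|---|---|---|---|
| Protocol measure, 30 refusals | 30/500 | 6.0% | 4.1–8.5% |
| Protocol measure, 60 refusals | 60/500 | 12.0% | 9.3–15.2% |
| SAP measure, either case | 100/500 | 20.0% | 16.6–23.8% |

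Refusal doubles and the SAP figure does not move. Over a wider assumed range (refusal 5% to 20%, other reasons 2% to 10%), refusal makes up between 0.05/(0.05 + 0.10) = 33% and 0.20/(0.20 + 0.02) = 91% of the SAP figure.

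**The case against.** The strongest reply is that this is a documentation gap and little more. SAP 6.3, Table 1.13 and Listing 1.4 already report reasons for withdrawal. The shells for Tables 2.49 to 2.54 are filed separately and might show reasons within those tables. The two proportions are descriptive, do not appear in the objectives and endpoints tables of either document, and have no bearing on the primary endpoint, kappa or sample size.

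Much of this stands, and it limits the point. A reader might infer that refusal is no longer estimated at all. The documents do not support that, for the reasons in step 4 of the working. What remains is that the dedicated proportions were dropped from the text that defines the analyses, and that indirect recovery depends on an eCRF category nobody can see in the plan.

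Other stronger readings also fail:

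- *Men seen after six weeks are counted as refusers.* No section makes a late visit a withdrawal. SAP Appendix 3 defines no analysis windows, and Appendix 1 handles out-of-window assessments as protocol deviations.
- *A man who declines PSA but receives a GP no is missed.* This is hypothetical. Protocol 4.1 places the GP's decision after the PSA result, so a man without one fits more naturally among those the GP could not assess, who are in the SAP numerator if they discontinue.
- *The urologist-stage denominator has changed in substance.* Protocol 4.1 sends every man with probable BPH to the urologist, so the two descriptions should cover the same men. Only the wording needs aligning.
- *A planned confidence interval was lost.* The two protocol sentences promise a summary and attach no interval.

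**Conclusion.** The point holds in a limited form. Following SAP 8.1.2 exactly produces a different quantity from the one planned in protocol 8.4.3, and SAP 2.1 is wrong to say nothing changed. The first part rests on comparing the two texts and on protocol 5.4 making withdrawal broader than refusal. The second rests on the documentation duty in protocol 8.4.

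The size of the discrepancy in this study is unknown. The calculated examples use assumed counts and show only that the SAP figure cannot reveal the refusal rate by itself. The consequence is confined to two descriptive secondary analyses, and the primary endpoint is unaffected. The change should be made because it is cheap and the no-change statement is incorrect.

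**What to change.** In SAP 8.1.2 and Tables 2.49 to 2.54:

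1. Add a row for refusal of further GP investigation, over all men with BPE/BPO ≥3.
2. Add a row for refusal of urologist referral, over men with BPE/BPO ≥3 and GP probable BPH.
3. Take both numerators from recorded withdrawal reasons. Confirm that refusal is identifiable among them; if it is not, say so in the SAP.
4. Keep discontinuation for any reason as a separate, labelled row.
5. Use one description of the urologist-stage denominator in the text, Table 4 and the table titles.
6. Correct SAP 2.1 to declare any difference from protocol 8.4.3 that remains.

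Exact 95% intervals on the new rows would be a reasonable addition, but the protocol does not ask for them. The cost is SAP wording and two table rows from disposition data. It is larger only if the eCRF does not record refusal, which the documents do not show.
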